## 10. Biospecimen Storage

No long-term storage of biospecimens is anticipated. Blood samples obtained at screening/baseline visit (for later assessment of Th2 immune deviation) will be stored in liquid N2 in the PIs laboratory. Similarly, nasal secretion/nasal sponge samples will be stored in a -20°C freezer in the PIs laboratory. The laboratory is always locked and is within a secured building (MR4 Bldg).

## 11. Criteria for Participant and Study Completion and Premature Study Termination

### 11.1. Participant Completion

Individuals will have completed their participation when they have completed all of their scheduled study visits.

### 11.2. Participant Stopping Rules and Withdrawal Criteria

Participants may be prematurely terminated from the study for the following reasons:

1. The participant elects to withdraw consent from all future study activities, including follow-up.
2. The participant is "lost to follow-up" (i.e., no further follow-up is possible because attempts to reestablish contact with the participant have failed).
3. The participant dies.
4. The Investigator no longer believes participation is in the best interest of the participant.
5. Individual safety stopping rules:
  - a. The participant develops a medical condition or is started on new medication(s) that, in the opinion of the investigator, may pose additional risks from participation in the study, may interfere with the participant's ability to comply with study requirements or that may impact the quality of the data obtained from the study.
  - b. A severe asthma exacerbation that requires treatment in the emergency room, hospitalization, or the use of systemic steroids, at any time during the study.
  - c. Use of a required but excluded medication such as inhaled corticosteroids or leukotriene modifiers.
  - d. Non-adherence to study procedures. Patients who miss visit 3 or 4 may be permitted to remain in the study as long as they comply with all other visits.
  - e. Pregnancy
  - f. Positive CoVID-19 test

### 11.3. Participant Replacement

If participants withdraw or are withdrawn, enrollment will continue until the numbers needed in each group complete the study.

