### 3. Study Design

#### 3.1. Description of Study Design

A total of 60 subjects will be enrolled in this open label challenge study over a period of 48-54 months (September 2016 – March 2021). These will include 20 subjects in each of 3 cohorts: healthy controls, allergic rhinitis controls, and asthmatics. At Visit 1 subjects will have baseline assessments of lung function and blood work. Viral inoculation will be performed on day 0 and assessments of cold and allergy symptoms, nasal viral titers, nasal mediators, lung function, and FeNO will be obtained on days 0 and days 1, 2, 3, 4, and 7 post-infection (dpi). In addition, methacholine challenges (days -7 and 4) will be performed. Finally, nasal biopsies will be performed on day 4 to assess extent of viral infection and nature of cell death (apoptosis v. necrosis). Each subject will complete the study at day 14.

Table I: Study Outline\*\*\*

Visit #:	1	2	3	4	5	6	7	8	9
	Day -7	Day 0	Day 1	Day 2	Day 3	Day 4	Day 7	Day 14**	Day 21
Symptom Assessment	X	X	X	X	X	X	X	X	X
Negative CoVID19 screen (afebrile/preserved sense of smell)	X	X	X	X	X	X	X	X	X
Pregnancy Test	X	X				X	X		
Viral antibody serology/CBC	X								
Virus inoculation		X							
Viral titers		X	X	X	X	X	X		
FEV1/ FeNO	X	X	X	X	X	X	X	X	
Nasal Scraping		X	X	X	X	X	X		
Nasal Washes / Sponge		X	X	X	X	X	X		
Nasal Biopsy						X			
Blood for Th immune deviation / AEC	X					X			
Methacholine Challenge	X					X			

\*\*\* If subject is still symptomatic at day 14 they will be contacted at day 21 with the possibility of an unscheduled visit. A Day 21 in-person visit will be scheduled if ANC or ALC falls below 500/ $\mu$ L, and does not return to baseline following the Day 14 blood draw. If disease activity increases after day 7 or other concerns arise either between visits 6 and 7 or after visit 8, participants will be instructed to contact study personnel and may be asked to return to the study site for an "unscheduled" visit.

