### Analysis Plan

#### 13.4.1 Analysis Populations.

Normal control subjects, allergic rhinitis controls, and asthmatics

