## **Appendix 1: Treatment Guidelines for Asthma Symptom Exacerbations**

### **Treatment guidelines should symptom exacerbations occur during the study:**

If a study participant experiences an increase in lower respiratory tract symptoms, or a decline in lung function, the following plan describes how subjects will be treated.

- For FEV1 value dropping between 20-29%20% from the baseline value not responding to albuterol, start on inhaled corticosteroids (Flovent 110 mcg./puff, 2 puffs bid) and discontinue when symptoms return to baseline.
- For FEV1 value dropping between 30- 49% from the baseline value not responding to albuterol, check oximetry and start on inhaled corticosteroid as above and 3 to 5 days of oral steroids (Prednisone 50 mg/day).
- For FEV1value dropping 50% or more from the baseline value. Transportation to the emergency room will be recommended and arranged. Individual stopping rules will apply as described in the Complete Clinical Protocol (Section 8.1.2). Further follow-up and management with the subject's primary care doctor; [name] and his study team will continue to be involved and available for follow-up and evaluation 30 days afterward for any subject who requires oral steroids, a visit to the ER, or hospital admission.

These treatment plans are in keeping with recommendations from the *Guidelines for the Diagnosis and Management of Asthma* (60).

**Note:** Baseline FEV1 values apply to the FEV1 measurements established at the scheduled visit with 2 days of RV-16 inoculation. Also note that young adults rarely become febrile during a natural or experimental infection with rhinovirus. However, if subjects develop a temperature greater than or equal to 101 degrees F, [name], together with back-up from the allergy fellow on call will be contacted (paged) for evaluation.\

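### Outcome-related withdrawal and replacement, with no all-inoculated analysis population, can trim the most affected asthmatics from primary endpoint 2

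*Combined protocol and SAP*

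**What the plan says.** Section 3.1 sets the cohort sizes: "These will include 20 subjects in each of 3 cohorts: healthy controls, allergic rhinitis controls, and asthmatics". Primary endpoint 2 compares lower respiratory symptoms (modified Jackson score and ACT) in asthmatics with those in the allergic rhinitis and healthy cohorts.

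Section 11.2 introduces its list with "Participants may be prematurely terminated from the study for the following reasons". Two of the individual safety rules in the list concern the lower airway or its treatment:
- item 5b: "A severe asthma exacerbation that requires treatment in the emergency room, hospitalization, or the use of systemic steroids, at any time during the study";
- item 5c: "Use of a required but excluded medication such as inhaled corticosteroids or leukotriene modifiers".

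Appendix 1 directs, for an FEV1 fall in its lowest band, "from the baseline value not responding to albuterol, start on inhaled corticosteroids". It adds oral steroids for a larger fall and emergency-room transfer for the largest.

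Section 11.1 defines completion: "Individuals will have completed their participation when they have completed all of their scheduled study visits". Section 11.3 sets replacement: "If participants withdraw or are withdrawn, enrollment will continue until the numbers needed in each group complete the study". Under Section 11.4 a withdrawn subject may be invited to one day 14 visit with ACT, auscultation and spirometry, and is asked to hand in the diary cards. No continued diary keeping and no nasal sampling are listed.

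The whole of Section 13.4.1 on analysis populations reads: "Normal control subjects, allergic rhinitis controls, and asthmatics". Section 13.1 offers multiple imputation only where it is judged necessary. Section 13.4.2 analyses the cumulative score (CLRTS) as a sum over days 0-4 and over days 0-7, and the daily scores by a GEE with working independence.

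**The concern.** The steroid treatment that Appendix 1 prescribes for a poor response to RV is itself a ground for termination under items 5b and 5c. Whether a subject's data stop is therefore linked to the response that endpoint 2 is meant to measure, and the link acts almost wholly in the asthma cohort. The study is open label, so the choice to terminate is made by someone who knows the cohort and has seen the response.

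There are two routes to bias, both toward no difference. First, nothing prevents an analysis of the 20 who complete, without the subject who was replaced. Second, even if that subject is kept, no rule covers the days after withdrawal, so the cumulative sum can be short. At stake is the size of the asthma effect on a primary endpoint for which the plan states no power.

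**Working it through.** **The plan's own figures.** Section 13.7 gives detectable factors for IL-25 and viral load only, at 20 per group, two-sided 0.05/3 and power 0.80. The normal approximation is SD × (2.394 + 0.842) × √(2/20). It gives exp(0.123) = 1.131 for SD 0.12, and 10^1.35 = 22.4 for SD 1.32. The t-test version (38 df) gives 1.136 and 25.35, against the stated 1.14 and 25. Both tables reproduce. Neither covers endpoint 2.

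**How many asthmatics.** Rates of steroid treatment in earlier challenges come from Sections 1.3 and 5.1. Expected number = 20p; chance of at least one = 1 − (1 − p)^20; limits are exact 95%.

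| Source | p | Expected in 20 | Chance of ≥1 | Upper limit, in 20 |
|---|---|---|---|---|
| RV-16, any steroid, 0/16 | 0% | 0 | – | 4.1 |
| RV-16 or RV-39, oral, 1/45 | 2.2% | 0.44 | 36% | 2.4 |
| RV-39, inhaled, 1/19 | 5.3% | 1.05 | 66% | 5.2 |

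That is about 0 to 1 of 20, with upper limits of about 2 to 5. Section 5.1 itself allows that including controller-treated asthmatics could bring more severe exacerbations.

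**Effect of exclusion, worst case.** Day 0-4 CLRTS means are from Section 1.3: 4.2 in 6 high-IgE asthmatics, 1.0 in 10 low-IgE asthmatics, 0.4 in controls.
- Asthma mean: (6 × 4.2 + 10 × 1.0)/16 = 2.2. Ratio to controls: 2.2/0.4 = 5.5.
- Asthma dispersion, from the day-21 intervals: k = n·se² − 1/mean, with se = ln(upper/lower)/3.92. High IgE: 6 × 0.396² − 1/13.5 ≈ 0.9. Low IgE: 10 × 0.495² − 1/8.5 ≈ 2.3.
- Control dispersion: 0.5, assumed.
- Simulation: negative binomial scores, the highest-scoring share of asthmatics removed and replaced, 20 per group, Wald test of the log ratio at two-sided 0.0167. This simplifies the planned GEE.

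| Removed | k = 0.9: mean; ratio; power | k = 2.3: mean; ratio; power |
|---|---|---|
| none | 2.20; 5.5; 0.93 | 2.20; 5.5; 0.80 |
| 2.2% | 1.98; 5.0; 0.90 | 1.85; 4.6; 0.74 |
| 5.3% | 1.79; 4.5; 0.86 | 1.54; 3.9; 0.63 |
| 10% (assumed) | 1.55; 3.9; 0.77 | 1.22; 3.1; 0.46 |

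With the day 0-21 means (10.4 against 0.7), the ratio falls from 14.9 to 10.7-12.4 at 5.3% removed and power stays above 0.99. The planned windows end at day 7, however, and no earlier day 0-7 figure is given.

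**Effect of truncation.** If a subject is withdrawn on day 3 and keeps no further diary, days 0, 1 and 2 remain. That is 3 of the 5 days in the first sum and 3 of the 6 in the second. Section 1.3 puts peak symptoms at 48-72 hours, and Section 5.1 places the earlier inhaled-steroid case at peak symptoms, so rescue can fall at or just before the day 3-4 focus of Section 13.4.2. An unweighted working-independence GEE is not protected when missingness depends on earlier scores.

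**The case against.** The strongest reply is that the plan nowhere discards anyone. Termination is permissive, Section 11.3 governs when recruitment ends and not whose data count, and a withdrawn asthmatic still belongs to the asthma cohort named in Section 13.4.1. Section 11.4 asks for the diary cards and includes ACT, which are the two components of endpoint 2, and imputation is available. Section 12.8.2.2.1 also suspends enrollment for DSMB review after a severe exacerbation, so such a subject is not replaced unnoticed. All of this stands, and it is why the bias is possible and not certain. It does not settle the matter: the visit is optional, diaries need not continue, imputation is discretionary, and no sentence says that withdrawn subjects are analysed.

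A reader might infer that the completing asthmatics would be non-responders. The documents do not support that. In the earlier RV-16 study 13 of 16 asthmatics had lower respiratory symptoms and none needed steroids, so none would have met the steroid grounds.

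A reader might also infer that IL-25 and viral load are understated. No passage or calculation shows that rescued subjects have higher values of either.

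The size can fairly be questioned too. Both steroid cases followed RV-39, not the study strain, and Appendix 1 acts on FEV1, not on symptom rank, so the tabulated losses are upper bounds for a given share removed.

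**Conclusion.** The concern holds in limited form. The plan joins outcome-related withdrawal, replacement to a completing number and an undefined analysis population, and so can cut the upper tail of the asthma cohort and pull endpoint 2 toward no difference. On the protocol's rates the likely number is 0 to 1 of 20. If that share is removed exactly from the top and wholly excluded, the day 0-4 mean falls by 10-16% at 2.2% and by 19-30% at 5.3%. The difference between cohorts shrinks but does not vanish. These figures rest on the worst-case ranking, the back-calculated asthma dispersions, the assumed control dispersion, and earlier rates carrying over to this population. The change should be made because it is cheap and the plan has no stated power margin on this endpoint.

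**What to change.** 1. In Section 13.4.1, define the primary analysis population as all inoculated subjects, each in his or her cohort.
2. In Section 11.3, state that anyone enrolled after a post-inoculation withdrawal is additional and does not displace the withdrawn subject. Report how many were added, and why.
3. In Section 11.4, separate stopping study procedures from stopping data collection. With the subject's agreement, continue daily diaries to at least day 7 and the scheduled non-invasive assessments.
4. In Section 13.4.2, analyse all observed scores for endpoint 2, including those after rescue. Pre-specify how missing days enter CLRTS, for example by multiple imputation. Keep a worst-score or worst-rank analysis as a sensitivity analysis, since as the primary one it could overstate asthma symptoms in an open-label comparison.
5. Reconcile Sections 7.3, 7.4, 11.2 (5b, 5c) and Appendix 1, which treat steroids in turn as prohibited, as rescue and as a ground for withdrawal. No clinical rule is proposed here.

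The cost is protocol and SAP wording, a few incomplete nasal-sample series, and slightly more follow-up and analysis work.

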### 11.4. Follow-up after Early Study Withdrawal

If a participant is withdrawn from the study for any reason, the participant may be asked to complete a final visit and/or final assessments. This will consist of a day 14 visit where participant will be asked about any adverse events and will be paid according to a pro-rated scale. They will be asked to turn in their diary cards and will be evaluated for presence and severity of asthma exacerbation. This will include:

- Administration of ACT
- Limited physical examination (auscultation)
- Spirometry

### 11.5. Study Stopping Rules

The enrollment and dosing of RV-16 in the study may be suspended pending review by the NIAID DSMB and the University of Virginia IRB for the following reasons:

- Any subject has a severe asthma exacerbation that requires treatment in the emergency room or hospitalization
- $\geq 2$  subjects experience severe asthma exacerbations requiring oral corticosteroids for  $\geq 5$  days, pending further expedited review.
- Any subject treated for pneumonia
- Any subject dies until expedited review is completed to determine whether the death might have resulted from any of the study procedures.
- Complications post biopsy requiring an urgent care visit in  $\geq 2$  subjects.
- Any death that occurs in the study, which is possibly or definitely related to study treatment regimen.
- The occurrence of a Grade 3 or higher related SAE in 2 or more of the study participants who have received a study treatment.

## 12. Safety Monitoring and Reporting

### 12.1 Overview

This section defines the types of safety data that will be collected under this protocol and outlines the procedures for appropriately collecting, grading, recording, and reporting those data. Adverse events that are classified as serious according to the definition of health authorities must be reported promptly (per Section 12.5, *Reporting of Serious Adverse Events and Adverse Events*) to the sponsor [DAIT/NIAID]. Appropriate notifications will also be made to site principal investigators and UVA Institutional Review Board (IRB).

Information in this section complies with *ICH Guideline E2A: Clinical Safety Data Management: Definitions and Standards for Expedited Reporting*, *ICH Guideline E-6: Guideline for Good Clinical Practice*, 21CFR Parts 312 and 320, and applies the standards set forth in the National Cancer Institute (NCI), Common Terminology Criteria for Adverse Events (CTCAE)..

### 12.2 Definitions

#### 12.2.1 Adverse Event (AE)

Any untoward or unfavorable medical occurrence associated with the subject's participation in the research, whether or not considered related to the subject's participation in the research (modified from the definition of adverse events in the 1996 International Conference on Harmonization E-6 Guidelines for Good Clinical Practice) (from OHRP "Guidance on Reviewing and Reporting Unanticipated Problems Involving Risks to Subjects or Others and Adverse Events (1/15/07)" <http://www.hhs.gov/ohrp/policy/advevntguid.html#Q2> )

For this study, clinical situations are listed that are considered to be outside the normal range of outcomes and will be recorded as Adverse Events. These situations do not limit an investigator from recording and reporting any other events, associated or not with these procedures as AEs:

**Study therapy regimen:**

- Rhinovirus-16 administration  
Rhinovirus infection is expected to result in cold symptoms among all subjects, and mild asthma symptoms among the asthmatic cohort. In addition, neutropenia and lymphopenia are expected within the first week after rhinovirus inoculation without clinical consequence. Upper and lower respiratory symptom data will be recorded on the RV Dairy Symptom Cards completed by study participants. An adverse event will be recorded in the following circumstances –
  - Treatment with an antibiotic or inhaled or systemic corticosteroid
  - Drop in lung function to  $\leq 70\%$  of predicted or ACT score  $< 19$
  - Febrile Neutropenia (ANC  $< 1000/\mu\text{L}$  with a single temperature of  $> 38.3$  degrees C (101 degrees F) or a sustained temperature of  $\geq 38$  degrees C (100.4 degrees F) for more than one hour)
  - Lymphopenia (ALC  $< 800/\mu\text{L}$ )
  - Any cytopenia with appropriate associated symptoms

**Study mandated procedures:**

- Spirometry / exhaled breath nitric oxide (FeNO) – Wheezing or bronchoconstriction requiring treatment with bronchodilators within 30 minutes from the procedure, Coughing requiring treatment with bronchodilators within 30 minutes from the procedure
- Methacholine challenge - Wheezing or bronchoconstriction requiring treatment with bronchodilators within 30 minutes from the procedure, Coughing requiring treatment with bronchodilators within 30 minutes from the procedure
- Nasal scrapings – Active epistaxis within 24 hours after the procedure lasting longer than 1 hour
- Nasal wash / sponge – Acute sinusitis diagnosed by a study clinician or based upon assessment of outside health records within 72 hours after the procedure
- Nasal biopsy - Active epistaxis within 24 hours after the procedure lasting longer than 1 hour, or infection needing medical treatment. Vasovagal symptoms and/or vasovagal syncope that do not respond to lowering of the participant's head
- Phlebotomy - Fainting/vasovagal event; Bruising at puncture site larger than 2 cm diameter, Bleeding from puncture site lasting longer than 5 minutes, Swelling at puncture site larger than 2 cm

Events not related to study participation will be recorded on the Adverse Events form if deemed to be Grade 2 or higher in severity.

**12.2.2 Suspected Adverse Reaction (SAR)**

Any adverse event for which there is a reasonable possibility that the investigational drug [or investigational study therapy regimen] caused the adverse event. For the purposes of safety reporting, ‘reasonable possibility’ means there is evidence to suggest a causal relationship between the drug and the adverse event.

A suspected adverse reaction implies a lesser degree of certainty about causality than adverse reaction, which means any adverse event caused by a drug (21 CFR 312.32(a)).

**12.2.3 Unexpected Adverse Event**

An adverse event or suspected adverse reaction is considered “unexpected” if it is not consistent with the risk information described in the Investigational Brochure.

Expected Risks related to Rhinovirus-16 inoculation and infection:	Frequency

 
• A decline in absolute blood neutrophil counts within first week following inoculation
 
• Bacterial sinus infection
 
• Lower respiratory tract infection (bronchitis)
 
• Lymphopenia within first week following inoculation
 
	
 
• Occurs frequently, but not known to be clinically significant.
 
• Occurs infrequently.
 
• Occurs infrequently. Rhinovirus is not known to cause pneumonia.
 
• Occurs infrequently, and not known to be clinically significant
 

 
• Cold symptoms could cause severe wheezing and shortness of breath, requiring additional; treatment
 
	
 
• Occurs infrequently
 

Expected Risks related to Spirometry Testing (excluding use of Methacholine)	Frequency

 
• Mild light-headedness and coughing
 
	
 
• Occurs frequently,
 

 
• Chest soreness
 
• Mild respiratory fatigue
 
• Mild shortness of breath
 
• Chest Tightness
 
• Fainting
 
	
 
• Occurs rarely
 

Expected Risks related to use of Methacholine	Frequency

 
• Mild asthma symptoms
 
	
 
• Occurs frequently,
 

 
• Coughing
 
• Fainting
 
• Chest tightness
 
• Shortness of breath
 
• Wheezing
 
	
 
• Occurs infrequently
 

 
• Bronchoconstriction
 
	
 
• Occurs frequently
 

Expected Risks related to Albuterol (if needed following Methacholine testing)	Frequency

 
• Headache
 
• Dizziness
 
• Insomnia
 
• Tremor
 
• Sweating
 
• Nausea
 
• Vomiting
 
• Dry Mouth
 
• Increased pulse rate
 
• Mild throat irritation
 
• Cough
 
	
 
• Occurs infrequently
 

 
• Allergic reaction
 
• Chest pain
 
	
 
• Occurs rarely
 

Expected Risks related to Nasal Washes / Nasal Sponge / Nasal Scraping	Frequency

 
• Discomfort during the nasal wash procedure
 
• Mild coughing
 
	
 
• Occurs infrequently
 

Expected Risks related to Nasal Scrapings	

 
• Mild to moderate discomfort for 30 seconds during the procedure
 
• Sneezing
 
• Epistaxis
 
	
 
• Occurs frequently
 
• Occurs frequently
 
• Occurs infrequently & easily stopped with standard treatment (external pressure applied to the nose).
 

Expected Risks related to nasal biopsy/administration of oxymetazoline, epinephrine (1:100,000), 4% lidocaine, and silver nitrate cautery	Frequency

 
• Pain/tenderness at biopsy site
 
	
 
• Occurs frequently
 

 
• Epistaxis
 
	
 
• Occurs infrequently & easily stopped with external pressure applied to nose
 

 
• Infection
 
	
 
• Very rarely
 

 
• Cardiac arrhythmias / palpitations
 
	
 
• Occurs very rarely or never at the study doses.
 

 
• Runny nose
 
	
 
• Occurs frequently
 

 
• Vasovagal symptoms and/or vasovagal syncope
 
	
 
• Occurs infrequently
 

Expected Risks related to Blood Draws	Frequency

 
• Pain at venipuncture site
 
	
 
• Occurs frequently
 

 
• Bruising at venipuncture site
 
• Fainting
 
	
 
• Occurs infrequently
 

 
• Infection
 
	
 
• Very rarely
 

